7.1 Concomitant Medications

7.1.1 Protocol-mandated

Not applicable

7.1.2 Other permitted concomitant medications

Not applicable

7.2 Prophylactic Medications

Infectious disease prophylaxis will be determined by the treating transplant physician.

7.3 Pre-Exposure Prophylaxis or Treatment of COVID-19 Infection

Per the Emergency Use Authorization, the participants in this study should not receive any pre-exposure prophylaxis (PrEP) e.g. tixagevimab plus cilgavimab (Evusheld™, AztraZeneca) during the 2-week period following any dose of COVID-19 vaccine. From a study perspective, it would be best to delay administration of any PrEP until after the Day 30 post-vaccine visit, when the primary endpoint is collected. If the participant or his/her treating physician feels it is in the patient's best interest to administer PrEP before Day 30 following the study dose of vaccine, we ask that the study team be informed since this will impact subsequent study evaluations, in particular antibody testing.

If a participant has a known exposure to COVID-19 and/or develops COVID-19 infection, treatment should be prescribed as clinically indicated by the participant's primary provider.

Administration of PrEP or any treatment of COVID-19 will be captured in the clinical database.

7.4 COVID-19 Vaccine Booster Doses

Participants should consult with the study team regarding non-study COVID-19 booster doses in order to maintain compliance with current CDC recommendations, while not compromising participation in the research study. Current CDC recommendations can be found at the following link:

<https://www.cdc.gov/vaccines/covid-19/clinical-considerations/interim-considerations-us.html#immunocompromised>

Current recommendations may change over the course of the CPAT-ISR study.

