2.5 Secondary Immunogenicity Objectives

To assess whether responses to additional doses of COVID-19 vaccine are improved by temporary reduction or withholding of immunosuppressive medications around the time of vaccine.

To assess whether response to an additional dose of COVID-19 vaccine is associated with clinical phenotype (e.g., age, organ type, time post-transplant, immunosuppressive regimen).

To evaluate durability of response over 1-year in those who have an antibody response to the additional dose of vaccine.

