3.3.2 Secondary Efficacy Endpoints

Duration of anti-SARS-CoV-2 S antibody titers and antibody neutralization in the year following the additional dose of vaccine
SARS-CoV-2 PCR positivity
Symptomatic COVID-19
COVID-19 requiring hospitalization
Longitudinal changes in log SARS-CoV-2 antibody titer during the study

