11.1 Participant Completion

All participants will be followed for 12 months following the COVID-19 vaccine administration.

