13.2 Endpoints/Outcomes

The primary endpoint is the proportional increase in antibody titer U/mL (using the Roche Elecsys® anti-RBD assay) at 30 days after the study dose of vaccine. Negative or very low antibody responses (<10 U/mL) will be imputed to 10 U/mL, to reduce the influence of measurement error on the proportional increase calculation among individuals with very low titers. Secondary safety endpoints include: local and systemic vaccine reactogenicity and/or allergy; serious adverse events occurring during the 30 days following the additional COVID-19 vaccine dose; treated acute cell-mediated and/or antibody-mediated allograft rejection (clinical or biopsy-proven) within 60 days following the COVID-19 vaccine dose; development of de novo donor-specific anti-HLA antibody within 90 days of the vaccine; graft loss within 60 days of the vaccine; and death within 60 days of the vaccine. Secondary efficacy endpoints include: SARS-CoV-2 PCR positivity; symptomatic COVID-19; COVID-19 requiring hospitalization; and longitudinal changes in SARS-CoV-2 antibody response during the study.

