13.4 Analysis Plan

13.4.1 Analysis Populations.

For the primary outcome and each secondary outcome, the analysis population will consist of all individuals with a measurement for that outcome, in an intent-to-treat framework.

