Appendix 2: Schedule of Events (COVID-19 Vaccine Dose Alone)

Study Schedule	Days		Weeks						Months				
Time points	0	3 ¹	1	2	3	4	5	6	3	6	9	12	For Cause ²
Visit #	01	02	03	04	05	06	07	08	09	10	11	12	FC
Visit Windows (+/-)	-	1d	1d	3d	3d	3d	3d	3d	2w	2w	2w	2w	-
General Assessments													
Study Contact ³	X		X	X	X	X	X	X	X	X		X	X
Medications (immunosuppression, PrEP, COVID-19 treatment)	X ⁴	→	→	→	→	→	→	→	X	X ⁵	X ⁵	X ⁵	X
Assessment of Events (AE, SAE, rejection, graft loss)	X	→	→	→	→	→	→	→	→	→	→	X	X
Clinical Laboratory Assessments													
Complete Blood Count with differential	X			X		X			X	X		X	
Metabolic Panel ⁶	X								X	X		X	
eGFR, serum creatinine (kidney)	X		X	X	X	X	X	X					
Hepatic Panel including direct bilirubin (liver)	X									X			
Quantitative Immunoglobulins	X									X			
SARS-CoV-2 PCR (nasal swab, clinical)	X ⁷					X			X	X	X	X	X
Investigational Intervention													
COVID-19 mRNA Vaccine	X												
Central Laboratory Assessments													
SARS-CoV-2 PCR (nasal swab, research)	X					X			X	X		X	X
Oral fluid anti-N and anti-S immunoglobulin levels	X					X			X	X		X	X
Anti-SARS-CoV-2 S (Roche Elecsys®)				X		X			X	X		X	X
Donor Specific Antibodies (kidney only)						X			X	X		X	X
Antibody/Neutralization assays	X			X		X			X	X		X	X
Spike Protein (subset of sites)	X	X											
Proteomics	X	X ⁸				X							
Transcriptomics	X	X ⁷				X							
T and B Cell Assays	X			X		X			X	X		X	X

¹ May be a home draw. The spike protein will only be performed at a subset of clinical sites.

² Unscheduled "for cause" visit for suspected rejection. Participants with confirmed COVID-19 will send in a nasal swab for research.

³ Study contacts may be remote.

⁴ Ensure the participant has not taken any medications since screening that would make them ineligible.

⁵ Only PrEP and COVID-19 related treatment collected at these visits.

⁶ Comprehensive metabolic panel at baseline, basic metabolic panel all other timepoints (see study definitions).

⁷ If the Day 0 nasal swab is positive, the participant will be prematurely discontinued and followed until Day 30 for safety. This includes the Day 30 clinical labs, DSA and AE/SAE assessment. No further mechanistic blood will be collected.

⁸ These Day 3 assessments will only be collected on participants included in the Day 3 spike protein.

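### One-year durability titres can include the effect of off-study boosters that the plan does not provide for recording, and no analysis rule covers titres taken after a booster, PrEP or infection

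*Combined protocol and SAP*

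**What the plan says.** Section 2.5 sets the objective: "To evaluate durability of response over 1-year in those who have an antibody response to the additional dose of vaccine". Section 3.3.2 makes it a secondary efficacy endpoint: "Duration of anti-SARS-CoV-2 S antibody titers and antibody neutralization in the year following the additional dose of vaccine". Section 13.2 carries the related endpoint as "longitudinal changes in SARS-CoV-2 antibody response during the study". Under Section 11.1, "All participants will be followed for 12 months following the COVID-19 vaccine administration". Both schedules (Appendices 2 and 3) draw the Roche anti-S titre at Weeks 2 and 4 and at Months 3, 6 and 12.

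On off-study boosters, Section 7.4 says: "Participants should consult with the study team regarding non-study COVID-19 booster doses in order to maintain compliance with current CDC recommendations". It adds that participation in the research should not be compromised and that the recommendations may change during the study. It states no recording rule.

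On PrEP, Section 7.3 says that from the study's viewpoint "it would be best to delay administration of any PrEP until after the Day 30 post-vaccine visit". It warns that PrEP given before Day 30 will affect later antibody testing, and it commits to capturing PrEP and COVID-19 treatment in the database.

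The schedules' medication row covers immunosuppression, PrEP and COVID-19 treatment. Footnote 5, at Months 6, 9 and 12 in both arms, narrows it: "Only PrEP and COVID-19 related treatment collected at these visits".

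For the analysis, Section 13.4.1 states that "the analysis population will consist of all individuals with a measurement for that outcome, in an intent-to-treat framework". Section 13.4.3 gives methods for binary endpoints and severe adverse events only.

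**The concern.** The objective is about the response to one particular dose. A later booster, an anti-spike antibody product or an infection can each raise the same anti-S titre. If such events are neither identified nor handled in the analysis, a late titre no longer measures persistence of the study-dose response.

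The protocol applies this reasoning at entry. Inclusion criteria 7 and 8 require at least 60 days since the last vaccine dose at the time of the study dose. They also require a qualifying titre taken at least 30 days after the last mRNA dose and at least 30 days after a monoclonal antibody or convalescent plasma. Nothing equivalent covers follow-up titres.

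Two results are at stake: the durability estimate within each arm, and the comparison between arms. Participants and clinical staff know the assignment, so booster or PrEP uptake could differ by arm.

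**Working it through.** **Plan's own figure.** None is given for durability. The only effect size, in Section 13.7, is 80% power for a 20% difference in fold change (3-fold against 2.5-fold, ratio 1.2) at Day 30. That is a different endpoint and serves below only as a yardstick.

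**Step 1: what is recorded and what is ruled on.**

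| Event after Day 0 | Foreseen in | Provision for recording | Rule in Section 13 for later titres |
|---|---|---|---|
| Non-study booster | 7.4 | None found in 7.3, 7.4, 8.3.3 or the schedules | None |
| PrEP | 7.3 | 7.3; kept by footnote 5 at Months 6, 9 and 12 | None |
| COVID-19 treatment | 7.3 | 7.3; kept by footnote 5 | None |
| SARS-CoV-2 infection | 8.3.3, 8.6 | eCRF; clinical PCR at Months 1, 3, 6, 9 and 12 | None |

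For boosters both the record and the rule are missing. For the other events only the rule is missing.

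**Step 2: which titres are exposed.** No anti-S titre is drawn between Months 3 and 6 or between Months 6 and 12. Suppose a response fades after the Month 3 draw and the participant is boosted before the Month 6 draw. The titres at Months 6 and 12 are then raised, and the data contain nothing to show why. If the booster comes after the Month 6 draw, that draw still shows the loss and only Month 12 is affected.

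**Step 3: illustration of size.** The documents give no uptake and no booster fold rise, so both are assumptions. Let b be the fraction boosted before the draw and F the fold rise still present at the draw (no waning).

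- Within an arm, the geometric mean titre is multiplied by F^b. With b = 0.3 and F = 2.5: 2.5^0.3 = 1.32. With b = 0.7 and F = 3: 3^0.7 = 2.16. The values 2.5 and 3 are borrowed from the Day-30 example in Section 13.7; they are not data on boosters.
- If true Month 12 retention of the Day-30 geometric mean is 25% (assumption) and b = 0.3, apparent retention is 0.25 × 5^0.3 = 40% at F = 5 and 0.25 × 10^0.3 = 50% at F = 10.
- Between arms, the ratio is multiplied by F^(difference in b). The uptake difference that produces a spurious 1.2 is ln 1.2 / ln F: 0.199 at F = 2.5, 0.166 at F = 3 and 0.079 at F = 10.
- The direction is open. Take a true ratio of 1.5 (IS reduction to vaccine alone). Uptake of 30% against 50% gives 1.5 × 5^(−0.2) = 1.09 or 1.5 × 10^(−0.2) = 0.95. Uptake of 40% against 30% gives 1.5 × 5^0.1 = 1.76 or 1.5 × 10^0.1 = 1.89. Equal uptake with equal F leaves 1.5.

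**The case against.** Several points on the other side stand.

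- A reader might infer that footnote 5 forbids collecting boosters. It does not. It narrows one row, which never contained vaccines, by dropping immunosuppression at late visits. The evidence is silence, and the schedules do not list everything collected: Section 13.4.4 uses the date of the last pre-study dose, although no schedule row names vaccination history. A case report form outside these documents might collect booster dates, and Section 7.4 has participants consult the study team. So it cannot be said that the information is irrecoverable, only that nothing in the documents provides for it.
- A reader might infer that participants are steered towards PrEP. Section 7.3 asks only that any PrEP be deferred. Because PrEP is recorded, the affected titres can be identified.
- A reader might infer that immunosuppression changes go unrecorded from Month 6. Section 8.3.3 has participants asked about immunosuppression at follow-up visits, and Section 8.4 tells them to report changes. The text supports only an inconsistency between footnote 5 and Section 8.3.3.
- Section 13.4.1 defines which individuals are analysed; no sentence says that titres after a booster are retained. Keeping all titres is also a legitimate intent-to-treat choice. Even so, that analysis cannot be interpreted without booster counts by arm, and it answers a different question from persistence of the response to the study dose.
- The illustration assumes uptake, borrows or assumes the fold rise and ignores waning, and the 1.2 yardstick belongs to the Day-30 endpoint.

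**Conclusion.** The concern holds in a limited form. Off-study boosters are accommodated during a year in which durability is an endpoint, the documents make no provision for recording them, and no rule covers titres after a booster, PrEP or infection. Followed as written, late titres can mix the study-dose response with later antibody, and booster-affected titres could not be identified from the data the plan provides for.

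The size is unknown. The figures above show that modest uptake differences could matter if the fold rise is large and persists; they do not estimate what will happen. The bias in the arm comparison can run either way and vanishes if uptake and fold rise are equal.

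It would go too far to conclude that the trial cannot say how long the response lasts. Month 3 and Month 6 titres still inform durability, and PrEP and infections are identifiable. The Day-30 primary endpoint is largely unaffected, apart from any PrEP given before Day 30. This should be corrected, but it does not threaten the main result.

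**What to change.** 1. Add non-study COVID-19 vaccine doses (date and product) to the medication row in Appendices 2 and 3, collected at every existing contact through Month 12, and amend footnote 5 to match. State the same commitment in Section 7.4.
2. Reconcile footnote 5 with Section 8.3.3 on whether immunosuppression is collected at Months 6, 9 and 12.
3. In Section 13.4.3, pre-specify a durability analysis that uses each participant's titres up to the first non-study booster, anti-spike antibody product or documented SARS-CoV-2 infection. Report it beside the all-titres analysis, with counts of each event by arm.

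None of this alters who may receive a booster or PrEP, or when. The cost is one eCRF item at contacts that already take place, a footnote and a paragraph of analysis text. The statistical price is fewer contributing titres at Months 6 and 12 and censoring that may be informative, since participants with low titres may be more likely to seek a booster. The all-titres analysis helps to show how much that matters.

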7.5 Rescue Medications

Not applicable

8. Study Procedures

8.1 Enrollment

Potential study participants may be identified by medical chart review and initially contacted by a member of the study team in person or over the phone. During this initial contact, the potential participant will be provided information on the study and asked about their interest in study participation. If they elect to continue, they will be consented to the SARS-CoV-2 S antibody testing using the Roche Elecsys® assay.

Potential participants with eligible SARS-CoV-2 antibody results will receive a concise and focused presentation of key information about the clinical trial, verbally and with a written consent form. The research study will be explained in lay terms to each potential research participant. The potential participant will sign an informed consent form before undergoing any study procedures.

8.2 Screening Period

The purpose of screening is to confirm eligibility prior to the study intervention.

Initial Screen

Chart review for eligibility

Blood drawn locally for anti-SARS-CoV-2 S (using Roche Elecsys® assay). A prior result may be used for eligibility if it was obtained at least 30 days following the last dose of mRNA COVID-19 vaccine administration and ≥ 30 days following receipt of a monoclonal antibody product or convalescent plasma for COVID-19.

Screening Procedures (Appendix 1)

The following procedures, assessments, and laboratory measures will be conducted to determine participant eligibility:

Review medical history and immunosuppression medications.

Blood drawn for detection of de novo DSA (central lab).

Research blood (central lab)

Serum creatinine, eGFR (for kidney recipients)

Hepatic panel, direct bilirubin, and INR (for liver recipients)

Confirm with the patient's transplant physician that they are eligible for IS reduction based on medical history, and that their physician concurs with the plan for IS reduction.

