3.2 Primary Endpoint

The primary endpoint is the -fold increase in antibody titer (using the Roche Elecsys® anti-SARS-CoV-2 S assay) from before receiving the study dose of vaccine to 30 days after the study dose of vaccine.

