8.7 Visit Windows

Study visits should take place within the time limits specified below: the designated visit windows (*i.e.* +/- *n* days) for each scheduled visit are also indicated on the Table of Events.

Screening	-30 days for screening clinical laboratory assessments SARS-CoV-2 S antibody at least 30 days following last dose of COVID-19 vaccine -90 days for dnDSA
Day 3, Week 1	+/- 1 day
Weeks 2, 3, 4, 5, and 6	+/- 3 days
Months 3, 6, 9, and 12	+/- 2 weeks

9. Mechanistic Assays

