13.4.2 Primary Analysis of Primary Endpoint(s)/Outcome(s)

The primary endpoint is a continuous measurement. All individuals whose primary endpoint is measured will be included in the analysis population.

For the comparison of immunoreduction vs no immunoreduction, we will reject the null hypothesis if the two-sided rank-sum p value comparing the -fold increase between the two groups falls below 0.05.

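### The primary fold-rise has no defined baseline titre, and Day 30 titres drawn after antibody prophylaxis have no analysis rule

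*Combined protocol and SAP*

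**What the plan says.** **Baseline.** Section 3.2 defines the endpoint as a fold increase "from before receiving the study dose of vaccine to 30 days after the study dose of vaccine". Section 13.2 restates it ("The primary endpoint is the proportional increase in antibody titer U/mL") and sets titres below 10 U/mL to 10. Neither says which pre-dose sample, laboratory or date supplies the denominator.

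In Appendices 2 and 3 the central-laboratory row beginning "Anti-SARS-CoV-2 S (Roche Elecsys" is marked at Weeks 2 and 4, Months 3, 6 and 12, and for cause. It has no mark at Day 0, or at Day -5 in the reduction arm. A separate row for antibody and neutralization assays is marked at Day 0 but names no assay. Section 8.3.2 has research blood drawn on Day 0 before vaccination.

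The scheduled pre-dose Roche test is the screening one in section 8.2, which is drawn locally. An earlier result is acceptable: "A prior result may be used for eligibility if it was obtained at least 30 days following the last dose of mRNA COVID-19 vaccine". Section 8.2 also requires 30 days since any monoclonal antibody or convalescent plasma. The window in section 8.7 is "SARS-CoV-2 S antibody at least 30 days following last dose of COVID-19 vaccine". Other screening laboratory tests there have a 30-day limit and donor-specific antibody a 90-day limit.

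**Day 30 value.** Section 7.3 says PrEP should not be given in the two weeks after vaccination, prefers that it wait until after Day 30, and allows it earlier if the participant or physician judges it best. It asks to be told because "this will impact subsequent study evaluations, in particular antibody testing". Section 13.4.2 has no corresponding rule: "All individuals whose primary endpoint is measured will be included in the analysis population".

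**The concern.** A fold-rise is only as good as its two titres, and here each has a gap.

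For the denominator, the only Roche value that the plan guarantees before the dose may be weeks or months old by Day 0. Titres wane at different rates over different intervals, and an unnoticed infection may raise them. Dividing a central Day 30 value by such a result adds variation unrelated to the study dose. The stated power makes no visible allowance for this.

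For the numerator, an injected anti-spike antibody given before the Day 30 draw would be read as vaccine response. PrEP decisions come after randomization, and participants and clinical staff know the assignment. If use differs between arms, the primary comparison is biased and not merely noisier.

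**Working it through.** **1. The SD behind the plan's power.** Section 13.7 gives 400 participants (200 per arm), two-sided alpha 0.05, a rank-sum test, and 80% power for a fold-change ratio of 1.2 (3 against 2.5). It gives no SD, so the 80% cannot be reproduced independently, only solved backwards.

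- Noether's formula with equal arms: (P - 0.5) = (1.960 + 0.842) / sqrt(12 x 0.25 x 400) = 2.802 / 34.64 = 0.0809, so P = 0.581.
- Standardized difference: sqrt(2) x probit(0.581) = 0.289.
- Implied SD of log10 fold-rise: log10(1.2) / 0.289 = 0.0792 / 0.289 = 0.274.

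An efficiency-based calculation gives 0.276 log10 (0.636 on the natural-log scale). Simulated power at that SD is 80.2%.

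**2. Noise from an old denominator.** Assumptions, none from the documents: exponential waning with a half-life H of 60 to 120 days, and a gap from screening titre to Day 0 spread uniformly over 0 to G days.

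- Added SD = log10(2) x G / H / sqrt(12).
- Total SD = sqrt(0.274² + added SD²).
- Power = Phi(34.64 x (P - 0.5) - 1.96), with P = Phi(0.0792 / (total SD x sqrt(2))).

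| Gap G (days) | Half-life H (days) | Added SD | Total SD | Power for ratio 1.2 |
|---|---|---|---|---|
| 0-60 | 120 | 0.043 | 0.278 | 79% |
| 0-60 | 60 | 0.087 | 0.288 | 76% |
| 0-90 | 120 | 0.065 | 0.282 | 78% |
| 0-90 | 60 | 0.130 | 0.304 | 72% |
| 0-180 | 120 | 0.130 | 0.304 | 72% |
| 0-180 | 60 | 0.261 | 0.378 | 53% |

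Type I error is not disturbed. With added noise of 0.5 on the natural-log scale (0.5 / 2.303 = 0.217 log10), the simulated rate under the null was 5.2%.

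**3. PrEP before Day 30.** The documents give no PrEP rate and no size of effect on the titre, so these are scenarios.

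- *Unequal use, rank argument.* Suppose a fraction q of controls and no reduction-arm participants receive PrEP, and all of them rank at the top. With no true effect, P(reduction > control) = 0.5 - 0.5q. For q = 0.05 this is 0.475, a shift of 0.025 against the design shift of 0.0809, or 31% of it in the wrong direction. For q = 0.02 the share is 12%, and for q = 0.01 it is 6%.
- *Unequal use, simulation.* With a 10-fold rise after PrEP and 0% against 5% use, type I error was about 12-14% across runs, and power for a ratio of 1.2 was about 44%.
- *Equal use, same 10-fold rise.* There is no bias, but power is about 72% with 5% use in each arm and about 65% with 10%.

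Reversing the imbalance reverses the direction of the bias.

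**The case against.** **The denominator may not be the screening value.** A reader might infer from the empty Day 0 cell that the plan divides by the local screening titre. The documents do not say so. The prior-result sentence concerns eligibility only, research blood goes to the central laboratory at screening and again on Day 0, and an unnamed antibody assay is scheduled on Day 0. This stands: the supportable finding is an undefined baseline. It still needs correcting, because the endpoint requires the Roche assay and no pre-dose Roche test other than screening is scheduled.

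**The screening titre is not without any age limit.** It must fall at least 30 days after the last mRNA dose, so its age cannot exceed the time since that dose less 30 days. This stands too: what is missing is a fixed maximum.

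**An old baseline does not bias the comparison.** The screening titre precedes randomization, so its staleness balances between arms in expectation. An overstated Day 0 titre affects both arms alike. The 10 U/mL floor also removes waning below 10, which the table ignores. If the planners' SD already reflected screening baselines, the table counts that noise twice. All of this stands, and limits the denominator issue to power.

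**PrEP exposure may be small.** Section 7.3 confines it mainly to about Day 14 to Day 30, prefers delay and records all use. Including everyone measured is a recognizable intention-to-treat strategy. That answers the size, not the missing rule: the protocol itself says these titres are affected. A reader might take the 31% or the raised type I error as the expected bias, but the documents support neither the rate nor the direction.

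**Partial mitigation.** The synopsis lists log titre at 30 days as a secondary endpoint, which needs no baseline. It is absent from sections 3.3.2 and 13.2, and it does not remedy the primary.

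**Conclusion.** The concern holds in two distinct parts.

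First, the baseline of the primary endpoint is undefined, and the only scheduled pre-dose Roche result is a local screening or earlier value with no fixed maximum age. If that value is used, the consequence is lost power and not bias. Under the assumed half-lives, power is about 72-78% for gaps up to 90 days and 53-72% for gaps up to 180 days, against the stated 80%. These figures rest on a back-solved SD and assumed gaps, and show only that the loss could range from slight to serious.

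Second, PrEP before Day 30 is permitted, acknowledged to affect the measurement, and not addressed in the primary analysis. With open-label assignment, unequal use could bias the comparison. Its size and direction depend on PrEP rates that the documents do not give.

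Both should be settled before the primary analysis, because they determine how the single primary endpoint is computed.

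**What to change.** **1. Define the baseline.** Mark Day 0 in the Roche row of Appendices 2 and 3, run the assay centrally on the pre-vaccine Day 0 blood, and name that result in sections 3.2 and 13.2 as the primary baseline. Keep the screening titre for eligibility and stratification. For participants already enrolled, use stored Day 0 serum where available. Day 0 follows randomization and, in one arm, five days of reduced immunosuppression. A central Roche run on the screening research blood would give a pre-randomization check if that is a worry.

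**2. Prespecify the handling of contaminated titres.** State in section 13.4.2 that a Day 30 titre drawn after PrEP, therapeutic monoclonal antibody or convalescent plasma is not scored as vaccine response. One way is to set it to missing in a model that uses the Week 2 titre, and only when that titre was drawn before the antibody product. Report the all-measured analysis alongside. Do not simply substitute Week 2 for Day 30. That would mix time points within one endpoint, Week 2 coincides with the end of the reduction period, and its window runs to Day 17 (14 + 3), which can itself follow PrEP.

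**3. Add a sensitivity analysis** for infection or a non-study booster before Day 30.

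The cost is about 400 runs of an assay already in use on blood already scheduled, one schedule edit, and a few sentences in the analysis plan. Section 7.3 already has PrEP and COVID-19 treatment recorded in the database.
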